### **2.1.2.2 DURATION OF SYMPTOMS RATED ‘MODERATELY BAD’ OR WORSE**

The predominant symptoms are scored daily on a scale from 0 to 6 (0 = no problem, 1 = very little problem, 2 = slightly problem, 3 = moderately bad, 4 = bad, 5 = very bad, and 6 = as bad as it could be). The scale is taken from a validated measure (Watson et al. 2001). The duration of symptoms rated ‘moderately bad’ or worse by patients after antibiotic treatment will be derived from the day 1-28 symptom diary question “*Tell us how bad these symptoms are today by ticking the box for your chosen number that fits best with how you are feeling*” which is completed after each antibiotic prescription. The number of days the patient answered, “moderately bad” (score = 3), “bad” (score = 4), “very bad” (score = 5), or “as bad as it could be” (score = 6) for the first antibiotic prescription event from the diaries will be calculated.

If the patient did not complete all their symptom diaries the day 28-30 post antibiotic telephone call will be used. At the day 28-30 call, participants are asked if their symptoms have resolved, and if they did resolve, how many days did it take for the symptom to become a minor problem or less (Variables *SYMP1RESLV SYMP2RESLV SY1RESLNUM SY2RESLNUM*). If the patient indicated on the call that the symptom did not resolve this outcome will be coded as 28 days.

If a patient had a prescription event that required diary completion, but they did not fill out any diaries or complete the 28-30 call this outcome will be missing.

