### 5.2 CONTINUOUS OUTCOMES

The continuous secondary outcomes:

- Duration of symptoms rated ‘moderately bad’ or worse,
- Number of days of antibiotic use (total and split by penicillin and non-penicillin, and antibiotic class)
- Defined daily dose (DDD) (total and split by penicillin and non-penicillin and antibiotic class),
- And length of hospital stays,

will be analysed using a linear mixed effects regression model. The models will include randomised group, age, number of antibiotic prescriptions in the 24 months prior to randomisation (12 months for those recruited to the nested pilot study), and the number of QOF registered diseases as fixed effects. GP practice will be included as a random effect. The adjusted mean difference between the randomised groups with 95% confidence intervals and P-values will be reported.

The proposed analyses assumes that these secondary outcomes satisfy the assumptions of the linear mixed effects regression model. Histograms of the distribution of each outcome split by randomised group, and post estimate plots of the residuals will be presented. If the post estimate plots show evidence that the assumptions of the linear mixed effects regression model have been violated, transformation of the data will be attempted. If there is still evidence that the assumptions have been violated a quantile regression will be implemented. The quantile regression will include randomised group, age, number of antibiotic prescriptions in the 24 months prior to randomisation (12 months for those recruited to the nested pilot study), number of QOF registered diseases, and GP practice as covariates. The adjusted median difference between the randomised groups with

95% confidence intervals, and P-values will be reported. If the quantile regression does not converge an unadjusted quantile regression will be attempted; if the model still does not converge a non-parametric approach such as a Mann-Whitney U test will be adopted.

Defined daily dose (DDD) split by class, is expected to be small for some classes in each randomised arm. If it is judged to be too small this will only be presented descriptively.

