## 14 APPENDICES

### 14.1 APPENDIX I. OBJECTIVES AND OUTCOME MEASURES

Objectives	Outcome Measures	Timepoint(s) (if applicable)
Primary Objective  Effects of PAAP on penicillin prescribing	Primary Outcome Measures  The proportion of participants who receive prescriptions for a penicillin when attending for predefined conditions where a penicillin is the first-line recommended antibiotic (Appendix II) up to 12 months post randomisation (SystmOne report/notes review/report, patient follow-up calls)	Up to 12 month post-randomisation  Primary Endpoint: Up to 12 months post randomisation
Secondary Objectives  1. To determine whether the PAAP intervention is clinically effective in improving patient health outcomes   2. Effects of PAAP on symptom duration	Secondary Outcome Measures  1. Treatment “response failure” defined as: Re-presentation with worsening or non-resolving or new symptoms following treatment with an antibiotic up to 28 days after initial antibiotic prescription (including re-prescription of antibiotic within 28 days of an index prescription) for predefined infections (SystmOne report), up to 12 months post-randomisation (primary and secondary notes review)  2. Duration of symptoms rated ‘moderately bad’ or worse by patients after antibiotic treatment (diary/research nurse telephone calls)	1. Timepoint: Each antibiotic prescription for predefined conditions prompts diary and patient reported outcomes collected for up to 28 days (or until symptoms resolve). Day 28-30 telephone call, will capture the primary outcome data as well.  Primary Endpoint: Up to 12 months post-randomisation   2. Day 1-28 symptom diary after the first antibiotic prescription identified as a primary event. This will also be collected at day 28-30 by phone call for every antibiotic prescription identified as a primary event

Objectives	Outcome Measures	Timepoint(s) (if applicable)
3. Effects of PAAP on total antibiotic prescribing	3. Total antibiotic use (measured by number of days treatment, number of prescriptions, and Defined Daily Dose (DDD)) and analysed by penicillin/non-penicillin and antibiotic class (SystmOne report/primary care notes review/secondary care notes review/report)	3. Up to 12 months post-randomisation

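### Symptom duration: an undefined incomplete diary is replaced by recall of a different quantity, and an unresolved symptom is coded 28 days even where recorded scores may show far fewer

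*SAP*

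**What the plan says.** Section 2.1.2.2 of the SAP uses a daily severity scale ("0 = no problem, 1 = very little problem, 2 = slightly problem, 3 = moderately bad", rising to 6). The outcome is the number of days scored 3 to 6, which "for the first antibiotic prescription event from the diaries will be calculated".

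The fallback rule is: "If the patient did not complete all their symptom diaries the day 28-30 post antibiotic telephone call will be used". The call asks whether symptoms have resolved and, if they have, "how many days did it take for the symptom to become a minor problem or less". If they have not: "If the patient indicated on the call that the symptom did not resolve this outcome will be coded as 28 days".

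The value is missing if the participant had an event that required a diary "but they did not fill out any diaries or complete the 28-30 call this outcome will be missing".

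Under section 5.2 the combined variable "will be analysed using a linear mixed effects regression model", with transformation and then quantile regression if the model assumptions fail. Section 6 restricts sensitivity analyses to the primary outcome.

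**The concern.** Three features of the derivation combine badly.

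- **The trigger is undefined.** The SAP does not say what a complete set of diaries is, how many blank days are tolerated, or what happens to the days that were filled in. On a strict reading, a single blank sets aside up to 27 recorded scores, although one blank leaves the true count uncertain by only one day.
- **The substitute is a different quantity.** The diary gives a count of days at or above a threshold. The call gives recalled elapsed time to a state whose label does not appear on the 0 to 6 scale.
- **The 28-day code does not use the outcome's own threshold.** A symptom at score 1 or 2 adds nothing to the diary count. It may nevertheless be unresolved on the call, and would then count as 28 days at moderately bad or worse.

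What is at stake is the meaning of the adjusted mean difference for this secondary outcome. The trial is open label, so both diary completion and recall could differ by arm. No planned analysis separates diary-derived from call-derived values.

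**Working it through.** The SAP gives no sample size, standard deviation, effect size or completion rate for symptom duration, so there is no figure of its own to reproduce. The check applies the section 2.1.2.2 rule to constructed diaries. Every diary pattern and rate below is an assumption.

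**1. Mild lingering symptom with one gap.** Assume score 4 on days 1 to 5, score 2 on days 6 to 28, and day 17 left blank.

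- Complete diary: 5 days.
- Recorded days with day 17 blank: 5, and at most 5 + 1 = 6.
- SAP rule, if one blank makes the diary incomplete and the participant says on the call that the symptom has not resolved: 28.
- Excess: 28 − 6 = 22 to 28 − 5 = 23 days.

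The same illness scores 5 with the blank filled in and 28 without it.

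**2. Count against elapsed time.** Assume scores of 3 or more on days 1 to 3 and 9 to 10, and lower scores on all other days.

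- Diary count: 3 + 2 = 5.
- Recalled time to a minor problem: 4 if the participant gives the first day at 2 or below, about 10 if the participant gives the last bad day.

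The two measures differ even when the symptom resolves and the 28-day code plays no part.

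**3. How often the call could replace the diary.** If all 28 entries are required and days are independent, the probability of a complete diary is r^28, where r is the daily completion rate.

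| Assumed r | r^28 |
|---|---|
| 0.90 | 0.05 |
| 0.95 | 0.24 |
| 0.98 | 0.57 |
| 0.99 | 0.75 |

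On the strict reading the fallback could be common. On a looser reading it would be rarer. The SAP does not settle which applies.

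**4. Effect on a mean.** Let q be the share of an arm with an incomplete diary, mild unresolved symptoms and a true count of 5. The shift in that arm's mean is (28 − 5) × q = 23q.

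- q = 0.10: 23 × 0.10 = 2.3 days.
- Between-arm difference in q of 0.02, 0.05 or 0.10: 0.46, 1.15 or 2.3 days of difference with no true effect.

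These figures show how the error scales. They do not estimate its size in this trial.

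**5. Whether the rest of the plan would expose it.** The section 5.2 checks may show a cluster at 28, and a median difference would be less sensitive to it. Neither a transformation nor a quantile model can recover the recorded scores that were replaced. Section 6 plans no diary-only analysis.

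**The case against.** Several stronger readings are tempting, and the SAP does not support them.

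- **That one missed day always discards the diary.** Section 2.1.2.2 never mentions a missed day. It also speaks of participants who filled out no diaries at all, which can be read as treating a diary as a whole unit. One missed day is one reading of an undefined term. What stands is that the term is undefined.
- **That mild lingering symptoms are always scored as the worst outcome.** A participant with a complete diary is scored correctly. For the rest, the result depends on what 'resolved' means on the call form, which is not shown. The follow-up question about becoming a minor problem suggests that the form may link the two. If so, a symptom at score 1 or 2 would count as resolved and would not be coded 28. The SAP does not state this, so the risk is possible but not established.
- **That Appendix I makes every recovered participant's diary incomplete.** The clause "patient reported outcomes collected for up to 28 days (or until symptoms resolve" sits in the timepoint for treatment response failure. The symptom-duration row refers to a day 1 to 28 diary without that clause. Stopping at resolution would also be a natural end to a diary, and a recovered participant moved to the call would report a number of days, not receive 28. The clause gives a reason to state the rule, but it is not evidence of inflation.
- **That the 28s go unchecked into a linear model.** Section 5.2 provides residual checks, transformation and quantile regression. This weakens the objection about extreme values but leaves the mixed measures in place.

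The call also has a proper use. A diary with three days at score 5 and then nothing would count only 3 days, even if the participant later reported no resolution. Using any diary, however short, would undercount such cases. Setting all unresolved cases without a diary to missing would remove people who may have had the longest symptoms.

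**Conclusion.** The concern holds in a limited form. For incomplete diaries, a term the SAP leaves undefined, section 2.1.2.2 replaces recorded daily scores with recall of a different quantity. It also assigns the maximum to an unresolved symptom without asking how severe that symptom is. Both follow from the text.

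The 28-day error for mild symptoms is conditional. It arises only with an incomplete diary, a report of no resolution, and a call form that does not define 'resolved' as below moderately bad. Where it arises, it can be large for the individual: 22 to 23 days in the assumed example. Its effect on the difference between arms is unknown. A reader might take 2.3 days as the expected bias, but that figure rests wholly on an assumed share and an assumed true duration.

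One secondary outcome is affected; the primary outcome is not. The derivation should be corrected before analysis.

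**What to change.** Amend section 2.1.2.2 as follows.

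1. Define diary completeness, including how many blank days count as isolated gaps.
2. Where the diary is complete, ends at recorded resolution, or has only isolated gaps, derive the outcome from the recorded days. State the gap rule and count days after recorded resolution as below 3.
3. Use the call only where the diary is absent, or stops early while symptoms are still scored 3 or more. Keep the 28-day code there only if no recorded score contradicts it.
4. State what 'resolved' and a minor problem mean on the call form in terms of the 0 to 6 scale.
5. Close the adjacent gaps: a partial diary with no call, a diary that breaks off at score 1 or 2 without recorded resolution, and how the two symptoms asked about on the call are combined.

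Add two sensitivity analyses for this outcome: one using diary data only, and one varying the value assigned to unresolved symptoms. Report by arm how many values came from the diary, from the call, and from the 28-day code.

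No new data are needed. The cost is slightly more derivation and programming work on one secondary outcome.

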The focus of ALABAMA is 'false positive' records of penicillin allergy, how these affect prescribing and whether a complex intervention aimed at correcting inaccurate records is clinically/cost effective. Patients with a penicillin allergy are usually not prescribed penicillins but instead receive alternative, broad-spectrum antibiotics which may lead to suboptimal therapy, be associated with poorer longer-term outcomes, and contribute to AMR (Charneski et al. 2011; Currie et al. 2014; Blumenthal et al. 2018; West et al 2019). Our preliminary research found macrolide, tetracycline, cephalosporin, quinolone, and clindamycin prescribing were all more common in patients with a record of penicillin allergy compared to those without, and that antibiotic prescriptions were almost twice as frequent in patients with a penicillin-allergy record (West et al. 2019). These differences were not explained by age, sex, or comorbidity. Systematic review evidence indicates that antibiotic-allergies affect health outcomes, increasing mortality, length of stay, and costs (Krah et al 2021 (<https://www.ncbi.nlm.nih.gov/pubmed/33059777>)). The large discrepancy between reported and true allergy rates suggests that introducing a 'pre-emptive' penicillin allergy assessment pathway (PAAP) for patients who are more likely to receive antibiotics, could impact upon antibiotic prescribing, yield patient benefits, limit AMR/Healthcare associated infection (HCAI), and deliver NHS cost savings.

Assessment of patients with penicillin allergy in specialist clinics is already provided within the NHS, but most who are eligible are not offered the service because of a lack of capacity (Krishna et al. 2017). Currently, penicillin allergy testing in many immunology/allergy clinics is performed over at least two clinic visits; the first, to undertake history and perform skin testing (ST); the second to assess reactions and undertake oral challenge testing (OCT) followed by communication of results. The allergy history is important to determine if the allergy history is spurious, of uncertain risk, low risk, or high risk of true penicillin allergy (Krishna et al. 2014). Skin testing and OCT may follow.

The ALABAMA trial approach will be different from this standard NHS practice in two ways:

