Regular reports were run in the ALABAMA unit to identify participants who had been prescribed an antibiotic, for any cause, in the previous 7 days. A member of the research team sent an alert to the trial research nurses team who then followed the participant up for the duration of the associated infection. The research team then designated an antibiotic prescription as a ‘primary event’ if the patient was prescribed an antibiotic for a pre-defined list of infections (see Appendix II). Participants receiving antibiotics for a primary event, were asked to complete a symptom diary. At the end of the follow up period their electronic health records were reviewed to ensure we had captured all antibiotic events. All trial participants had case note review and, if required had capture hospital episode statistics, and mortality data.

Throughout this process general practice staff and participants received behaviour change intervention materials.

See Appendix III for study flowchart.

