#### **2.1.2.3.1 NUMBER OF ANTIBIOTIC PRESCRIPTIONS**

This outcome will be derived from the notes review question “*Please list all the antibiotics the patient was treated with for the above event or symptoms*” (Variable *ABXNAME*), as well as data from the SystmOne report and hospital prescribing report (if available). This outcome will be derived as the number of antibiotic prescriptions up to 12 months post-randomisation. If there is no evidence of antibiotic usage this outcome will be coded as zero. A “prescription” will be considered to be an uninterrupted period of antibiotic use. Where a period of at least 2 days separates prescriptions for the same antibiotic, these will be considered separate prescriptions.

If the patient had a relevant infection event but there is no prescription data for that patient then this outcome will be missing. Patients who also withdrew before 12 months who do not have an antibiotic prescription, and who withdrew consent for notes reviews to be conducted will also have this outcome missing.

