## 2.3 SAMPLE SIZE

The primary outcome was initially treatment response failure defined as the percentage of re-prescription of an alternative antimicrobial within 28 days of an index prescription. A total sample size between 1592 and 2090 participants provided 80-90% power to detect a clinically important absolute difference of 7.9% in re-prescription rate at one year between groups (i.e. reducing from 19.8% in the control group to 11.9% in the PAAP group) at 5% level of significance (2-sided). The sample size had been adjusted assuming 50% of participants will require at least one prescription within 1 year from randomisation and allowing for 10% dropout. Participants are classed as enrolled at the point of randomisation.

The primary outcome was then changed to 'effects of PAAP on penicillin prescribing', defined as 'The proportion of participants who receive prescriptions for a penicillin attending for predefined conditions where a penicillin is the first-line recommended antibiotic (see Appendix II) during the course of routine primary care up to 12 months post randomisation. A total sample of 848 (i.e. 424 per group) was required to provide 90% power to detect an increase in the proportion of penicillin prescription from 4% (Usual Care) to 14% (PAAP) over the year after randomisation at 5% level of significance (2-sided) and 10% attrition. The sample size has been adjusted assuming 50% of participants will require at least one prescription within 1 year from randomisation. At 80% power, the sample size required was 656 (i.e. 328 per group). The table below also provides the sample size required if not all participants have reached 12 months follow-up.

Power	% Difference	Total sample size (all reached 12 months FU)	Total sample size (80% reached 12 months FU)	Total sample size (90% reached 12 months FU)
80%	10%	656	820	729
	15%	372	465	413
90%	10%	848	1060	942
	15%	472	590	524

Results from our recent analysis, using data extracted from the SystmOne database, suggested that there were an average of 110 patients per average practice size of 6000 who fulfilled our inclusion criteria.

- 1) Adults (over 18 years),
- 2) Penicillin allergy in electronic health records,
- 3) And in receipt of a penicillin, cephalosporin, tetracycline, quinolone, or macrolide class antimicrobial in the previous 24 months.

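### Symptom duration can be derived only after a post-randomisation antibiotic prescription, yet section 5.2 reports it as a difference between the randomised groups

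*SAP*

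**What the plan says.** - **Who gets a diary.** SAP section 2: "Participants receiving antibiotics for a primary event, were asked to complete a symptom diary". Primary events are antibiotic prescriptions for the infections listed in Appendix II.
- **What is counted.** Section 2.1.2.2 counts the days scored 3 or more, and the count "for the first antibiotic prescription event from the diaries will be calculated". Appendix I gives the timepoint as "Day 1-28 symptom diary after the first antibiotic prescription identified as a primary event". The fallback source, the day 28-30 call, is also made only after an antibiotic.
- **Missing data.** The only rule in section 2.1.2.2 begins "If a patient had a prescription event that required diary completion, but they did not fill out any diaries" and sets the outcome to missing if there was no day 28-30 call either. Nothing is said about participants with no event.
- **Analysis.** Section 5.2 lists the outcome for a linear mixed model and states: "The adjusted mean difference between the randomised groups with 95% confidence intervals and P-values will be reported". It names no subset and adds no caveat.
- **Comparable outcomes.** For the number of prescriptions, section 2.1.2.3.1 says: "If there is no evidence of antibiotic usage this outcome will be coded as zero". Treatment days, DDD, hospital admissions and hospital days also default to zero, and response failure is coded 0 when no source shows it.
- **Sensitivity analyses.** Section 6 restricts these to the primary outcome unless explicitly stated, and none is stated for symptom duration.

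**The concern.** A participant enters this comparison because of something that happens after randomisation and that PAAP may influence. Total antibiotic prescribing is secondary objective 3, so the SAP itself treats an effect on prescribing as an open question. The trial is open label, and section 2 says practice staff and participants receive behaviour-change materials.

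If the arms differ in who is prescribed an antibiotic, or for which infections, and that difference is related to how long symptoms last, the two sets of first events are not comparable. A difference in mean duration could then arise with no true effect on duration, or a true effect could be hidden. A reader of the section 5.2 result would take it for a randomised treatment effect with the usual protection.

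**Working it through.** **1. Share of participants with a value.** The SAP gives no figure for symptom duration, but section 2.3 plans the trial "assuming 50% of participants will require at least one prescription within 1 year from randomisation". Its sample size reproduces as follows.

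- Inputs: 4% versus 14%, two-sided 5%, 90% power, 1:1 allocation.
- The two-proportion formula gives 171 per arm, or 190 with continuity correction.
- 190 / 0.9 = 211.1, rounded up to 212 for attrition. 212 / 0.5 = 424 per arm, or 848 in total, as stated.
- At 80% power, 147 per arm leads to 656, also as stated.

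Of 848 randomised, 848 x 0.9 = 763 are followed and 763 x 0.5 = about 382 have a prescription, roughly 190 per arm. About half of those followed would have no symptom-duration value, before any loss from unreturned diaries or missed calls.

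**2. Size of a selection effect when PAAP has no true effect on duration.** The following are assumptions, not figures from the SAP: whether a first event occurs depends on a normal latent severity; that severity has correlation rho with symptom duration; SD of duration is 6 days; the same selection rule applies in both arms; and the share with an event is 50% in usual care (the planning figure) and p in PAAP.

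Mean shift among those with an event, in SD units = rho x phi(z_p) / p, where phi is the normal density and z_p is the cut-off exceeded with probability p.

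- p = 0.50: 0.3989 / 0.50 = 0.798
- p = 0.45: 0.3958 / 0.45 = 0.880, a difference of 0.082
- p = 0.40: 0.3863 / 0.40 = 0.966, a difference of 0.168

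| PAAP share | rho 0.3 | rho 0.5 | In days (x 6) |
|---|---|---|---|
| 45% | 0.025 SD | 0.041 SD | 0.15 to 0.25 |
| 40% | 0.050 SD | 0.084 SD | 0.3 to 0.5 |

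With rho = 0, or equal shares under the same selection rule, the result is 0. If the PAAP share rose instead, the sign would reverse.

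**3. Precision.** With 190 events per arm, SE = 6 x sqrt(2/190) = 0.62 day. With a 40% PAAP share (381 x 0.40 = 152 events), SE = 6 x sqrt(1/190 + 1/152) = 0.65 day. The illustrated bias is therefore below one standard error. At rho = 0.4 the two-sided type I error would be about 6% at a 45% share and about 10% at 40%, instead of 5%.

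**4. What coding no event as zero would do.** Assume a mean of 6 days in usual-care events, still with no true effect on duration. The usual-care mean over all participants is 0.50 x 6 = 3.0 days. At a 40% PAAP share it is 0.40 x (6.3 to 6.5) = 2.5 to 2.6 days. The difference is about -0.4 to -0.5 day, similar in size to the conditional bias and opposite in sign, because this measure also counts how often events occur.

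**The case against.** **The conditioning is visible.** The outcome is defined as duration after antibiotic treatment for a first event, and an episode that did not occur has no natural duration. Both points are fair. The definition is legitimate; what is wrong is presenting it as a comparison of the randomised groups.

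**Exclusion is not stated.** No sentence says that participants with no event are left out of the section 5.2 model. This stands: it is inferred from the derivation and from the absence of a zero rule. It is nevertheless the natural reading.

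**A stronger reading of section 1.3.** A reader might take the statement that "antibiotic prescriptions were almost twice as frequent in patients with a penicillin-allergy record" to mean that PAAP should roughly halve the share of participants with an event, and so cause a large bias. The SAP does not support this. The figure is an observational comparison of prescription counts, whereas this outcome uses only the first event, so repeat prescriptions do not alter who enters. Section 2.3 uses a single 50% share with no difference between arms, and objective 3 asks about total prescribing without predicting a fall.

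**Not every effect on prescribing biases the result.** A shift unrelated to symptom duration leaves the contrast unbiased.

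**Some checks are planned.** Sections 2.1.2.3.1 and 5.3 compare the number of prescriptions by arm. That would show whether prescribing moved, but not whether the severity or type of first events differs.

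**Conclusion.** The point holds as a matter of structure. Symptom duration can be derived only for participants with a first primary-event prescription after randomisation, and section 5.2 reports it as a randomised comparison with a P-value, no caveat and no sensitivity analysis.

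The documents do not establish that bias will occur, nor its direction or size. The illustrated 0.15-0.25 day (share falling to 45%) and 0.3-0.5 day (falling to 40%) rest on an assumed correlation, SD and PAAP-arm share. They are modest beside a standard error of about 0.6 day. The case for a change is that the result would carry an interpretation the design does not give it, and that the correction is cheap. One secondary outcome is affected.

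**What to change.** 1. In sections 2.1.2.2 and 5.2, state that the analysis is conditional on a first primary event and label it supportive, not a randomised treatment effect.
2. Report by arm the number and percentage with a first primary event and with a symptom-duration value, together with their baseline characteristics and infection types.
3. Add one supplementary analysis in all participants: symptom days in the first primary event, 0 if records show no primary event in 12 months, with the existing missing rule kept. Report a mean difference with robust standard errors. Do not apply section 5.2's median fallback, because with about half the values at zero both medians would sit at or near zero.
4. Describe that analysis as a combined burden of event frequency and duration that does not capture untreated illness, and show it beside the conditional result. As step 4 of the working shows, it cannot replace the conditional result.

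The cost is SAP wording, one descriptive table and one extra model. No new data collection is needed.
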